4.3.3. Pharmacokinetic studies

Pharmacokinetic studies will be performed in a maximum of 20 participants per treatment arm (520 patients in total). Upon oral intake, albendazole gets metabolized first to sulfoxide and further to sulfone, whereas the sulfoxide is thought to be the most active compound to treat STH infection. In order to evaluate potential differences of PK parameters, including the metabolization rate in different populations, all three compounds, namely albendazole, albendazole sulfoxide and albendazole sulfone, will be quantified with time. Two blood microsampling techniques, namely dried blood spot (DBS) and Mitra® are currently under investigation to quantify albendazole and its metabolites in human blood samples. Consequently, whole blood, plasma, DBS and Mitra® blood samples were collected in a previous clinical trial in rural Côte d'Ivoire with 10 adult volunteers who received the standard dose of albendazole. Methods to extract and quantify albendazole and its metabolites in all four matrixes are currently validated in order to demonstrate that the capillary and venous blood results correlate satisfactoryly. Once validation of the analytical method has been completed, the best blood micro-sampling device, DBS or Mitra®, will be chosen as a tool for these albendazole population pharmacokinetic studies in preschool-aged children, schoolaged children and adults.

In more detail, capillary blood (\pm 0.1 ml) will be collected by middle or ring finger tip puncture using a finger pricker (e.g. Accu-chek Softclix Pro®, Roche). Sampling will be conducted at 0, 1, 2, 3, 4, 6, 8, 24 hours post-dosing. The time points might be slightly adapted (shifted or reduced) in case the purpose for optimization is seen after the analyses of the samples of the 10 adult patients has been completed. A few drops of blood will be transferred at each time point on DBS filter paper (Whatman) or Mitra® microsampling device and dried for approximately 1 hour. The DBS cards or Mitra® will be transported to Swiss TPH in Basel and stored at -80° C until analysis. Albendazole and its metabolites will be quantified using a validated liquid chromatography tandem mass spectrometry (LC-MS/MS) method. Drug concentrations will be calculated by interpolation from a calibration curve with a foreseen limit of quantification of approximately 1-5 ng/ml. Quality control samples will be included in the study and its measured concentrations used to determine between-run and overall precision and accuracy of the analysis.

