4.3. Trial design

4.3.1. Baseline survey

Stool samples collection

Two stool samples will be collected from each participant until a total of 560 hookworm-infected participants (160 preschool-aged children, 200 school-aged children and 200 adults) and 480 *T. trichiura* infected participants (160 preschool-aged children, 160 school-aged children and 160 adults) are identified.

[figure not shown]
The Kato-Katz technique will be used for the quantitative assessment of STH infections. Two stool samples will be collected from each participant before treatment and from each sample duplicate Kato-Katz thick smears (41.7 mg each) will be prepared [8]. The slides will be analyzed under a microscope by experienced technicians and a subsequent independent quality control of sample results (approximately 10%) will be conducted. Results are considered correct if the following tolerance margin is not exceeded: (i) No difference in presence/absence of hookworm, A. lumbricoides and T. trichiura, (ii) egg counts are +/-10 eggs for counts ≤100 eggs or +/-20% for counts >100 eggs (for each species separately) [9]. In case discrepancies above the tolerance margin are noted in one or more slides, all slides are re-read by the local technicians. The new results are discussed, so that in case of discordant results, slides can be re-evaluated to reach consensus. Infection intensity expressed as the arithmetic and geometric mean egg counts per gram of stool (EPG) will be calculated for each treatment arm. All microscopically analyzed quadruplicate Kato-Katz thick smears will be destroyed within one day (after passing the quality control). Since drug efficacy could be influenced by genetic aspects, ~2 g of stool sample from each participant will be preserved in ethanol for further genetic analyses of hookworm and T. trichiura in Côte d'Ivoire and Switzerland.

[figure not shown]
Clinical examination and biological exams

At baseline, the medical history of *T. trichiura* and hookworm-infected participants in the study will be assessed with a clinical and physical examination carried out by the study clinician, who will assess weight, height, body temperature, pulse rate and blood pressure. Rapid diagnostic tests for malaria will be done to assess the presence of a *Plasmodium* spp. co-infection. Hemoglobin (Hb) levels will be detected using HemoCue to exclude severely anemic participants (below 80 g/l and 70 g/l Hb in school-aged and preschool-aged children,

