4.4. Measure to minimize bias

Study participants eligible for treatment will be randomly assigned to one of the treatment arms using a computer-generated, stratified block randomization code. The random allocation sequence with varying random blocks of 4 and 8 (or 5 and 10, respectively) stratified by 2 levels of baseline infection intensity (light and moderate *T. trichiura* and hookworm infections) will be provided by a statistician. Study-site investigators will be aware

of the study group assignment, whereas participants and laboratory technicians will be blinded.

Placebo controlled trials reduce the risk of potential bias that can also interfere with the observed outcomes. In previous studies (e.g. Coulibaly et al. 2017 Lancet Global Health), we have observed moderate cure and egg reduction rates in placebo treated children likely due to the low sensitivity of anthelminthic diagnostics. Children treated with placebo will be treated at follow up (3-weeks post treatment) with 400 mg albendazole. This treatment delay does not cause any harm.

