6.2. Methods of recording and assessing adverse events

Subjects will be kept for observation for at least 3 hours following treatment for any acute adverse events. If there is any abnormal finding, the local study physician will perform a full clinical and physical examination and findings will be recorded. An emergency kit will be available on site to treat any medical conditions that warrant urgent medical intervention. Adults, school-aged children and the mother of preschool-aged children will also be interviewed 3 and 24 hours after treatment and at follow-up (2-3 weeks after treatment) about the occurrence of adverse events (see chapter 4.6).

Information on all adverse events (onset, duration, intensity, seriousness and causality) will be immediately entered in the appropriate adverse event module of the case report form (CRF) that serves as source document. For all adverse events, sufficient information will be pursued and/or obtained so as to permit i) an adequate determination of the seriousness of the event (i.e. whether the event should be classified as a serious adverse event); ii) an assessment of the casual relationship between the adverse event and the study treatments and iii) an assessment of intensity of adverse events will be judged by the study physician.

All serious adverse events or SUSARs must be reported as described in Section 6.3.

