7.2. Justification of number of trial subject

Since the existence of a drug effect is well known, the main aim of the study is the elucidation of the nature of the dose–response relationship. A series of simulations was carried out to determine the required sample size. We assumed a true cure rate against hookworm of 5%, 30%, 50%, 70% and 80% (for 0, 200, 400, 600 and 800 mg) and of 5%, 10%, 20%, 30% and 40% against *T. trichiura* and loss to follow up of 5%. We estimated that enrolling 40 participants per arm will be sufficient to predict the dose response curve with a precision (defined as median distance between prediction and confidence band) of about 10 percentage points. The suggested sample size is also in line with the recommendations from Klingenberg et al. 2009 [11]. This sample size is sufficiently high to determine the key PK parameters as well as PK/PD relationships.

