7.3. Description of statistical methods

The primary analysis will use the full analysis set (available case population) according to the intention to treat principle defined as all randomized subjects which provide any follow-up data. Only subjects which were negative at baseline and erroneously randomized will be excluded from the analysis. In addition, a per-protocol analysis will be conducted. CRs will be calculated as the percentage of egg-positive participants at baseline who become egg-negative after treatment. EPG will be assessed by adding up the egg counts from the quadruplicate Kato-Katz thick smears and multiplying this number by a factor of six. The ERR will be calculated (ERR = (1-(mean at follow-up/mean at baseline))*100).

Geometric mean egg counts will be calculated for the different treatment arms before and after treatment to assess the corresponding ERRs. Bootstrap resampling method with 5,000 replicates will be used to calculate 95% confidence intervals (CIs) for ERRs point estimates. E_{max} models using the DoseFinding package of the statistical software environment R will be implemented to predict the dose-response curves in terms of CRs and ERRs.

On the basis of the LC-MS/MS measurements, the following PK parameters for plasma will be calculated:

C_{max} maximal plasma concentration

t_{max} time to reach C_{max}

AUC area under the curve, from 0 to 24h and 0 to inf

T_{1/2} elimination half-life

 C_{max} and T_{max} will be observed values derived from the plasma concentration time profile. AUC and $T_{1/2}$ will calculated with the software WinNonlin (Version 5.2, Pharsight Corporation, USA) using noncompartmental analysis. The elimination half-life will be estimated by the equation: $T_{1/2} = ln2/\lambda$, where λ will be determined by performing a regression of the natural logarithm of the concentration values during the elimination period.

Further PK analysis will be undertaken fitting a structural compartmental PK model with the software NONMEM 7 via nonlinear mixed effects modeling (allowing for both between patient variation and random effects). This model will describe the blood drug levels in time, allowing one to investigate variation between patients in drug levels. In addition, pharmacometric-pharmacodynamic (PKPD) analysis will be undertaken via NONMEM to investigate the drivers of cure and/or burden reduction and potentially any covariates with drug levels.

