10.6. Other aspects

We will include one arm of each study cohort treated with placebo. However, this group will be treated with a standard treatment of 400 mg single dose albendazole at the end of the study (3-4 weeks later); hence, this does not cause any medical concern. Patients generally are treated only in yearly intervals to reduce morbidity from chronic infections. A treatment delay of 3-4 weeks is not expected to cause any harm.

11. Quality control and quality assurance

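### Should the PK total of 520, which counts the six placebo arms, be cut to the 400 participants in the active arms?

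*Combined protocol and SAP*

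**What the plan says.** On the PK subsample, Section 4.3.3 says "Pharmacokinetic studies will be performed in a maximum of 20 participants per treatment arm (520 patients in total"). The times are fixed in the same section: "Sampling will be conducted at 0, 1, 2, 3, 4, 6, 8, 24 hours post-dosing", with about 0.1 ml of capillary blood each, and they may later be shifted or reduced. The analytes are albendazole, its sulfoxide and its sulfone.

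On the arms, Section 4.3.1 plans "a total of 560 hookworm-infected participants (160 preschool-aged children, 200 school-aged children and 200 adults") and 480 with *T. trichiura* (160 in each age group). Section 7.2 sets 40 per arm. Section 10.6 adds: "We will include one arm of each study cohort treated with placebo".

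On the use of the samples, Section 7.3 says "On the basis of the LC-MS/MS measurements, the following PK parameters for plasma will be calculated", and lists Cmax, tmax, AUC and half-life.

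On blinding and safety, Section 4.4 leaves site investigators aware of allocation, "whereas participants and laboratory technicians will be blinded". Under Section 6.2, adults, school-aged children and the mothers of preschool-aged children are "interviewed 3 and 24 hours after treatment and at follow-up (2-3 weeks after treatment) about the occurrence of adverse events".

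No readable section restricts PK sampling to albendazole arms, and none says outright that placebo participants are sampled. The cohort flow charts are not reproduced in the copy reviewed.

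**The concern.** A participant on placebo has no albendazole concentration from which to derive Cmax, tmax, AUC or half-life. If the total of 520 is taken at face value, placebo participants still go through the full sampling schedule. Most of them would be children, whom Section 10.5 treats as needing particular protection. Its reason for PK work in children, that PK differs between children and adults, does not reach a child on placebo. Blank samples would not need them either: the schedule in Section 4.6 places the 0-hour sample before treatment, so active participants already supply pre-dose blood.

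At stake are participant burden, laboratory work and clarity about who is sampled. The efficacy result is not at stake.

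**Working it through.** **Arm count** (doses from Section 3; cohort sizes from 4.3.1; 40 per arm from 7.2)

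| Cohort | Enrolled | Active arms | Placebo arms | Arms = enrolled / 40 |
|---|---|---|---|---|
| Hookworm, preschool | 160 | 3 | 1 | 4 |
| Hookworm, school-aged | 200 | 4 | 1 | 5 |
| Hookworm, adults | 200 | 4 | 1 | 5 |
| *T. trichiura*, preschool | 160 | 3 | 1 | 4 |
| *T. trichiura*, school-aged | 160 | 3 | 1 | 4 |
| *T. trichiura*, adults | 160 | 3 | 1 | 4 |
| Total | 1,040 | 20 | 6 | 26 |

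**The plan's figure.** 26 x 20 = 520, an exact match. None of the other counts tried gives 520:
- active arms only: 20 x 20 = 400
- arms pooled over parasite: 14 x 20 = 280, or 11 active x 20 = 220
- a 200 mg *T. trichiura* arm added for school-aged children and adults: 28 x 20 = 560, or 22 active x 20 = 440

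**Placebo share (upper bounds, because 20 is a maximum)**
- Participants: 6 x 20 = 120, made up of 40 preschool, 40 school-aged and 40 adults; 80 are children.
- Samples: 120 x 8 = 960 of 520 x 8 = 4,160, and 960 / 4,160 = 23.1%. In children: 80 x 8 = 640.
- Volume per person: 8 x 0.1 = 0.8 ml. Section 4.3.1 takes 4 ml of venous blood for biochemistry, assessed before treatment and again at 14-21 days.

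**What active-only sampling would gain.** Each active arm has at most 20 sampled participants under either rule. The PK parameters and the exposure data on albendazole are therefore the same at 520 and at 400. The only gain is the 960 samples not taken.

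**What it would cost in blinding.** The chance of being on active drug, for a participant who knows the sampling rule, is as follows for 4-arm and 5-arm cohorts.

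| Rule | Pricked | Not pricked |
|---|---|---|
| 20 in every arm (520) | 60/80 = 75%; 80/100 = 80% | 60/80 = 75%; 80/100 = 80% |
| 10 per placebo arm (460) | 60/70 = 85.7%; 80/90 = 88.9% | 60/90 = 66.7%; 80/110 = 72.7% |
| Active arms only (400) | 100% | 60/100 = 60%; 80/120 = 66.7% |

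With equal sampling, being pricked tells the participant nothing. With active-only sampling, it identifies active drug for half of each active arm (20 of 40). The 3-hour and 24-hour interviews fall within the sampling period.

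**What it would cost in balance.** Section 10.2 lists mild discomfort and weakness among the reactions to blood sampling, and Section 6.1.2 includes trial procedures among the factors in judging relatedness. Under active-only sampling, up to eight extra procedures would be given to 20 of 40 participants in each active arm and to none on placebo. Any procedure-related event would then count only against albendazole. The documents give no rate for such events, so the bias cannot be sized; its direction is clear.

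**The case for a change.** The strongest case for a change is that a procedure with no stated purpose should not be done in young children. The protocol never claims blinding or balance as its reason. Placebo exposure is known to be zero without an assay, and pre-dose samples and quality-control samples cover the laboratory's needs. The blinding loss may also be modest: participants already have a 75-80% chance of active drug, adverse events are analysed descriptively, egg counts are read by blinded technicians, and a participant who does not know the sampling rule can infer nothing.

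Part of this stands. The reason is missing, and a reader has to infer from the total that placebo arms are sampled. The rest does not force a change. Because site investigators know the allocation, participant blinding is the main protection for reported adverse events, and safety is a secondary objective. Keeping the sampling rule from participants raises a consent question that cannot be checked here, since the consent pages are not in the copy reviewed. The burden, up to 0.8 ml by finger prick, is small beside the venous sampling that everyone has.

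Sampling 10 per placebo arm is a preference between two reasonable designs; nothing in the documents favours 460 over 520.

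A related wish is to tie the adequacy statement in Section 7.2, "This sample size is sufficiently high to determine the key PK parameters as well as PK/PD relationships", to 20 per active arm instead of 40 per arm. No section justifies 20 for PK, so that edit would attach an unsupported claim to a different number.

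**Conclusion.** No change to the plan is needed. The total of 520 is arithmetically right for 26 arms. Counting the placebo arms costs at most 120 participants (80 children) and 960 samples, 23% of the total. It preserves participant blinding with respect to PK sampling and keeps procedures balanced across arms. Cutting to 400 would add no PK information and would give up both protections. The cure-rate analysis and the enrolment of 1,040 are the same either way.

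This rests on three assumptions: that the total means placebo participants are in fact sampled, which the text implies but does not state; that the maximum of 20 and all eight time points are used, so the figures are upper bounds; and that the missing flow charts do not restrict PK sampling to active arms. If they do, 520 is a clerical slip for 400 and the analysis is still unaffected. Stating in Section 4.3.3 whether placebo arms are included, and why, would be a useful but optional clarification.

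### Correlation between capillary and venous results cannot show that the chosen micro-sampling device gives the plasma exposures that Section 7.3 reports

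*Combined protocol and SAP*

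**What the plan says.** Section 4.3.3 explains that "whole blood, plasma, DBS and Mitra® blood samples were collected in a previous clinical trial in rural Côte d'Ivoire". The donors were ten adults, all given one dose level. The extraction and quantification methods for these four matrices "are currently validated in order to demonstrate that the capillary and venous blood results correlate satisfactoryly". Once that work is complete, "the best blood micro-sampling device, DBS or Mitra®, will be chosen as a tool for these albendazole population pharmacokinetic studies". The section gives no coefficient, cut-off, bias limit or limits of agreement, and does not define what makes a device best.

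The same section describes an LC-MS/MS method as validated, refers to a calibration curve, and adds QC samples, with their "measured concentrations used to determine between-run and overall precision and accuracy of the analysis".

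The concentrations have two uses. One is the exposure-response objective in Section 3, based on Cmax, AUC and tmax. The other is a comparison between populations: "In order to evaluate potential differences of PK parameters, including the metabolization rate in different populations", albendazole, its sulfoxide and its sulfone are all quantified over time. Section 7.3 presents Cmax, tmax, AUC and half-life as plasma parameters. Section 4.3.3 collects finger-prick blood dried on filter paper or a Mitra device, and neither section states a blood-to-plasma conversion.

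**The concern.** Correlation measures how tightly paired readings follow a straight line, whatever its slope or intercept. It says nothing about whether that line is the line of equality. Serial PK data make this worse: the rise and fall of the curve and the spread between people produce a wide range of concentrations, and a wide range pushes the correlation up.

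The stated aim could therefore be met without anyone learning the ratio of micro-sample to reference. That ratio is what is needed to call a dried-blood result a plasma Cmax or AUC, and to compare the two devices on accuracy. At stake are the absolute exposures, the metabolite ratios if the ratio differs by compound, and the child-adult comparison if it differs by age. The paired samples come from adults only.

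**Working it through.** **The plan's own figure.** Section 4.3.3 allows 20 PK participants per arm and 520 in total. *T. trichiura* has 3 cohorts × 4 arms = 12 arms; hookworm has 4 + 5 + 5 = 14. (12 + 14) × 20 = 520, which reproduces. Six of the 26 arms are placebo, so at most 20 × 20 = 400 participants have albendazole exposures resting on the device.

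**What correlation can see.** Let x be the reference reading and y the device reading. For any b > 0, corr(x, b·y) = corr(x, y). A device that reads b times too high or too low has exactly the correlation of an accurate one with the same random error.

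**What a constant factor does to the Section 7.3 parameters.**
- Cmax and AUC are multiplied by b.
- tmax is unchanged.
- Half-life is ln2/λ, with λ taken from the slope of log concentration. Since ln(b·C) = ln b + ln C, the slope and the half-life are unchanged.
- The ranking of participants by exposure is unchanged.
- A metabolite ratio is multiplied by b₁/b₂, where b₁ and b₂ are the factors for the two compounds. A child-to-adult exposure ratio is multiplied by b_child/b_adult. Both multipliers equal 1 unless the factors differ.

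**Illustration by simulation.** From the documents: 10 adults, and the trial schedule "Sampling will be conducted at 0, 1, 2, 3, 4, 6, 8, 24 hours post-dosing". Assumed: that this schedule also applied to the 10 adults (7 post-dose times × 10 = 70 pairs), one-compartment curves with between-person variation, venous error of 5%, device error of 10%, 15% or 25%, bias factors of 0.5 to 1.5, and a cut-off of r ≥ 0.90. There were 2,000 runs per setting. Results at 15% device error:

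| Device factor | Mean r | Runs with r ≥ 0.90 | Lin's concordance | Pairs differing by ≤ 20% of their mean | Geometric mean ratio |
|---|---|---|---|---|---|
| 1.0 | 0.958 | 99.8% | 0.954 | 79.7% | 1.00 |
| 1.3 | 0.958 | 99.9% | 0.838 | 34.6% | 1.30 |
| 1.5 | 0.959 | 99.9% | 0.725 | 9.7% | 1.50 |
| 0.7 | 0.958 | 100% | 0.795 | 16.0% | 0.70 |
| 0.5 | 0.958 | 99.9% | 0.527 | 0.1% | 0.50 |

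At 10% error r is 0.98 for every factor. At 25% error it is about 0.90 for every factor, and 54-57% of runs reach 0.90 whether or not there is bias. Correlation thus responds to random error but not to constant proportional bias.

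**Can 10 adults support a ratio?** The 90% CI of a geometric mean ratio multiplies and divides the estimate by exp(t × s/√10), with t = 1.833 on 9 degrees of freedom and s = √ln(1 + CV²). One log ratio per person is assumed.
- CV 15%: s = 0.149; exp(1.833 × 0.149/3.162) = 1.09.
- CV 35%: s = 0.340; exp(1.833 × 0.340/3.162) = 1.22.

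Under these assumed CVs the existing sample locates the ratio to within about 9% to 22%.

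**What the other checks cover.** The QC samples and calibration curve can reveal an extraction or calibration error in the assay. They do not pair a finger-prick sample with venous blood or plasma from the same person, so they cannot reveal a capillary-venous, haematocrit or blood-to-plasma difference.

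**The case against.** Section 4.3.3 states an aim for preparatory work then under way. It is not a decision rule. The verb may be loose wording for agreement, and a separate validation report may hold accuracy limits. Device choice follows validation of the methods in all four matrices, so assay accuracy is not ignored. One device is to serve all cohorts, and a constant factor would leave the exposure-response correlation as it was. PK is secondary. An agreement analysis in 10 adults could not exclude a bias specific to children.

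Most of this stands and limits the point. A reader might infer that the plan contains a pass mark that would admit a device misreading by 30-50%. It does not: the documents give no coefficient or cut-off and no sign that either device is biased, so the factors in the table only illustrate an identity. A reader might also infer that correlation is high for almost any device. At 25% error an accurate device misses 0.90 in about 45% of runs.

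The objection does not supply the missing ratio. The documents cite no agreement limit, and the plasma label in Section 7.3 needs either agreement with plasma or a stated conversion.

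**Conclusion.** The point holds in a limited form. Correlation is the only capillary-versus-venous criterion in the documents, and it cannot show that DBS or Mitra gives the reference concentration. The plasma label in Section 7.3 therefore has no stated support. That correlation is blind to a constant factor is exact and needs no assumption. The size of any actual error is unknown.

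The consequence is a possible common shift in absolute Cmax and AUC. Metabolite ratios and age comparisons are affected only if the bias differs by compound or by age, and the documents give no evidence that it does. The primary cure-rate analysis, tmax, half-life and exposure ranking are not affected by a constant factor. The change should be made before PK parameters are computed, but the point does not threaten the trial's main conclusion.

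**What to change.** In Section 4.3.3, replace the correlation aim with an agreement criterion for each compound and each device:

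- Name the reference matrix. Either use plasma, to match Section 7.3, or relabel the Section 7.3 parameters as whole-blood values.
- From the 10 adults, report the within-person geometric mean ratio of micro-sample to reference with its 90% CI, and the limits of agreement on the log scale.
- Choose the device on how close that ratio is to 1 and how stable it is across people and concentrations.
- If the ratio is stable but differs from 1, apply it as a stated conversion factor before computing PK parameters, and carry its uncertainty into the report.
- State that a ratio from 10 adults may not hold in children. Show the haematocrit distribution by age group, which Section 4.3.1 already collects, as a caveat to the child-adult comparison.

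The cost is a short text change and some re-analysis, plus a conversion factor whose uncertainty must be reported. No new sampling is needed, provided the four matrices were sampled at matching times in the 10 adults, which the protocol does not say.
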